12.4 Unscheduled visit

Unscheduled visits may be performed at any time during the clinical trial and will generally include the assessments listed in [Table 3](#). Depending on the reason for the unscheduled visit, further appropriate assessments maybe done according to the investigator's discretion. Results of the assessments and any change in concomitant medications will be recorded in the eCRF. After an unscheduled visit, the regular scheduled visits must continue according to [Table 3](#).

12.5 End-of-study (EoS, Day 28) and premature termination

Patients will undergo the assessments and procedures shown in [Table 3](#).

In case of premature discontinuation, assessments of the EoS visit should be performed at Day 28 for the respective patients, whenever possible. Patients who were discharged (*for centers in Bulgaria only: between Day 14 and 28*), will be asked to return at Day 28 for EoS assessments. If the patient dies during the trial, the investigator should indicate that this visit was not performed, however should fill out all information about patient status to be performed at the EoS visit. If the patient refuses any EoS visit or is lost to follow-up, at least the survival status should be ascertained e.g., by calling the patient, his/her relatives, or referring physician, or by searching registers or publicly available information for survival status information.

In case of premature withdrawal from the trial or IMP, reasons, circumstances and findings will be fully described on the corresponding page in the eCRF respecting the patient's rights.

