The first dose of IMP (2 tablets) should always be given on Day 0 (allowed range for first dose: 12:00 noon on Day 0 to 02:00 a.m.). All further IMP doses are 1 tablet each in the morning and evening. For details of IMP administration see Section 11.1.5. Information about the status and patient care are continuously obtained and documented once or twice daily (see [Table 3](#)). Further examinations and tests, laboratory parameters, biomarkers, disease markers, and virologic parameters are to be assessed as outlined in [Table 3](#).

After the last IMP dose in the evening of Day 13, the end-of-treatment assessments will be done on Day 14 (see [Table 3](#)). Blood sampling for IMU-838 trough values must be performed in the morning around the time the morning dose was usually taken by the respective patient. Patients may then continue to receive SoC without any further restrictions on concomitant medications as during the 14-day BT period (see Section 11.2.1 and [IMP-related exclusion criteria](#)).

The assessments to be performed in case of hospital discharge before Day 14 are described in Section 12.3. *For centers in Bulgaria only: Patients must be hospitalized during the entire treatment period i.e., from Day 0 to Day 14.*

Day 28 Visit (EoS)

The patient should return for the final trial visit on Day 28 (EoS). If IMP is prematurely discontinued for any reason, the EoS visit should always be conducted on Day 28 and no earlier EoS should be performed. If patients withdraw from IMP prematurely, they should be encouraged to allow the EoS visit as part of the follow-up. If the patient dies during the trial, the investigator should indicate that this visit was not performed. However, even if no EoS visit was performed, information about patient status should be reported on the EoS page in the case report form. If the patient refuses any EoS visit or the patient is lost to follow-up, it is permissive in this trial that the investigator contacts the patient, the family of the patient or the referring physician by phone or email to obtain status of life information, or is able to search in registers or publicly available information for such status of life information.

Safety follow up

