- l For assessments, if patients will be discharged from the hospital before Day 14, see *Blinded Treatment period (Day 0 to Day 13) and Day 14 (end-of-treatment)*. For centers in Bulgaria only: Patients must be hospitalized during the entire treatment period.
- m Within 4 days of randomization.
- n If no EoS visit was performed, information about patient status should be reported on the EoS page in the case report form. If the patient is lost to follow-up, the investigator must contact the patient, the patient's family or the referring physician by phone or email to obtain survival status, or it must be possible to search in registers or publicly available information for these survival data.
- o Blood sampling must be performed in the morning around the time the morning dose was usually taken by the respective patient.
- p Safety follow up assessments must be performed regularly (at least once) by phone or email between Day 28/EoS and Day 60 and documented as an unscheduled visit in the eCRF. The patients should be asked to return for an on-site visit if the investigator deems this necessary for follow-up. The assessments not to be done if the visit is performed as a telephone or email contact in the scope of the safety follow up are marked as •^p
- q *Optional for centers in the USA only: 2 blood samples will be collected to evaluate immune cell subtypes and immune reactions for future research studies. This will be shipped directly to a US research site and not to the central laboratory. Shipment needs to be done at ambient temperature and immediately the same day after sampling.*
- r Height and weight only to be measured at D0, pre-dose.

AE = adverse event, CT = computed tomography, cont. = continued, D = day, ECG = electrocardiogram, ECMO = extracorporeal membrane oxygenation, EoS = end-of-study, EoT = end-of-treatment, ICU = intensive care unit, Ig = immunoglobulin, IMP = investigational medicinal product, incl. = including, interst. = interstitial, pre(post) = pre(post) IMP, RRT = renal-replacement therapy, Radiol. = radiological, SARS-CoV-2 = severe acute respiratory syndrome coronavirus 2, SFU = safety follow up, SoC = standard of care, SpO₂ = peripheral capillary oxyhemoglobin saturation, ventil. = ventilation, USV = unscheduled visit, WHO = World Health Organization.

12.2 Screening (Day -2 to Day 0) and Day 0

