16.1 Sample size calculation

Part 1

As no formal hypothesis testing will be conducted in Part 1, no formal sample size calculation is deemed necessary. In previous protocol versions, a pooling of p-values of Part 1 and Part 2 was planned and a sample size of N = 200 enrolled patients (100 per group) was calculated. It is assumed that with the previously planned sample size a robust estimation of all efficacy and safety parameters can be conducted. Thus, no adaptations in sample size for Part 1 are necessary.

Previously, the following assumptions were made:

3-stage group sequential adaptive test design with O'Brien and Fleming shaped boundaries

Information rate for Part 1 analysis: 0.2

O'Brien and Fleming alpha level for end of Phase 2 analysis: <0.0001

Primary endpoint: Proportion of patients without any need for invasive ventilation

Randomization ratio: 1:1 (45 mg/day IMU-838:placebo)

Power: 80%

Global significance level: 0.05, 1-sided

Proportions of patients with need for INV

for 45 mg/day IMU-838:	32%
for placebo:	40%
Number of patients (Part 1):	188

Considering a 6% drop-out rate, a total of 200 patients (100 per group) were to be enrolled.

Part 2

If the trial is expanded to Part 2, the sample size of Part 2 will be determined based on the results of MA1.

The Part 2 (Phase 3, Expansion Phase) trial will be designed to keep a global 1-sided alpha level of 0.025 (one-sided). A 2-stage group sequential test adaptive design with O'Brien and Fleming shaped boundaries will be used. Stage 1 will be IA2 applying an overall information rate of 50% and using an alpha of 0.0026. The use of group sequential boundaries within the context of an adaptive design is enabled using the inverse normal method, combining the p-values of both stages with weights based on the sample sizes. Statistical analysis methods that control for the Type I error will be used.

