16.3.2 Primary and key secondary efficacy endpoint analyses

In the following the analyses for the primary and key-secondary endpoints are described for Part 1. Since Part 1 and Part 2 will be independent parts, these endpoints may be changed for Part 2 after the MA1 analysis. More details and/or changes for evaluation in Part 2 will be specified in a protocol amendment and respective SAP when MA1 results are available.

Primary endpoint

The primary endpoint of the trial i.e., the proportion of patients without any need for INV until EoS. The “need for INV” (considered positive for the primary endpoint) will include patients:

1. placed on any INV method during the trial
2. who had an active “do not intubate” or “do not resuscitate” order established during the trial conduct or refused intubation for any reason but were assessed by the investigator to have a medical need for INV
3. who had a medical need for INV as assessed by the investigator but for reasons of medical resource exhaustion or due to triage decisions by the hospital had not received INV, or
4. who died mainly due to respiratory failure but had a need for INV as assessed by the investigator or before such needed INV could have been started

Patients who are lost to follow-up or discontinue the trial on or before Day 13 (last treatment day) due to any reason other than death and discontinue with a last observed WHO clinical status no lower than that at Screening, and patients who die and do not fall under Number 4 of the above-mentioned criteria will be considered treatment failures for the primary endpoint. A sensitivity analysis will be performed for patients who discontinued before EoS, using the available information on INV.

Invasive ventilation involves any instrument penetrating via the mouth (e.g., endotracheal tube), nose, or the skin (e.g., tracheostomy tube through a stoma) to serve as an artificial airway, and the manual or mechanical ventilation of the patient through such artificial airway.

For clarification, bilevel positive airway pressure (trademarked as BiPAP™ or VPAP™ by different manufacturers) and continuous positive airway pressure are not considered INV as they do not involve intubation. However, for classification of patient clinical status these methods are considered non-invasive ventilation (WHO Status 5, [Table 4](#)).

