Patients who discontinued the trial before Day 28 due to any other reason than death will be considered as deaths, unless survival status can be obtained by the investigator through other means (see Section [12.4](#)).

In a sensitivity analysis, patients who discontinued before EoS due to reasons other than death, will be considered as survived, unless the investigator has any information of patient death after discontinuation.

In Part 2, the primary endpoint (as selected during MA1) and the key secondary endpoints that include proportion of patients (e.g. patients without respiratory failure, 28-day all-cause mortality) will be evaluated for superiority of IMU-838 vs placebo with an exact Cochran-Mantel-Haenszel test, adjusted for the stratification factors age and antiviral therapy. In addition, logistic regression analyses will be conducted including the covariates age, antiviral therapy, sex, and country. The distribution of primary endpoint or any key secondary endpoint containing duration measurements (e.g. duration of ICU treatment) will be analyzed with the van Elteren test (stratified by age and antiviral therapy). In addition, time-to-event analyses using Kaplan Meier methodology and a stratified log rank test (stratification factors age and antiviral therapy) will also be performed. All tests will be performed 1-sided keeping a global alpha level of 0.025 (1-sided).

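### Section 16.3.2 imputes failure for unimproved early leavers even when their ventilation status to Day 28 is known, and no passage on a missed Day 28 visit tells sites to ask about it by phone

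*Combined protocol and SAP*

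**What the plan says.** **Contact when the Day 28 (end-of-study, EoS) visit is missed.** The strength of the duty differs by place.

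- Synopsis and Section 8.1: allowed. "it is permissive in this trial that the investigator contacts the patient, the family of the patient or the referring physician by phone or email", for life status.
- Section 12.5: advised. "at least the survival status should be ascertained e.g., by calling the patient, his/her relatives, or referring physician". The same section asks for the EoS assessments at Day 28 after premature discontinuation where possible.
- Table 3 footnote n (also in Table 1): required. "the investigator must contact the patient, the patient's family or the referring physician by phone or email to obtain survival status". The footnote is attached to the survival-status row.

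Section 17.2 adds reasonable efforts to reach lost patients, complete assessments and recover missing data. After withdrawal of consent nothing more is collected, unless the patient allows non-interventional follow-up.

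**Main-analysis rules in Section 16.3.2.**

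- Primary endpoint: patients who are lost or leave on or before Day 13 for a reason other than death, and who "discontinue with a last observed WHO clinical status no lower than that at Screening", are failures.
- Respiratory failure: the same two conditions, but joined so that they can be read as two separate groups. The result is again failure.
- ICU duration: the same group as for respiratory failure. The stay is run to Day 28, from discontinuation if no ICU stay is known and from actual admission otherwise.
- Mortality: counted as a death, "unless survival status can be obtained by the investigator through other means".

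**Sensitivity analyses in Section 16.3.2.** INV and respiratory failure are re-analysed with the available information. One ICU analysis uses information only up to the day of discontinuation.

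**The concern.** Of the four endpoints at the top of the hierarchy, only mortality lets a known outcome override the imputed one. Suppose a patient leaves the trial on Day 4 with unchanged WHO status, agrees to non-interventional follow-up and is seen on Day 28, never having needed ventilation. The main analysis still scores this patient as a failure. If the patient is instead reached through a relative or physician, nothing tells the site to ask about ventilation, so the sensitivity analysis may have nothing to use.

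Part 1 has no formal test, so type I error is not at issue. At stake are the estimates and their 90% intervals. The main analysis of Part 1 (MA1) judges activity on observed relative differences, and the observed proportions then feed the Part 2 sample size (Section 16.4.2).

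**Working it through.** **1. The plan's own figures (Section 16.1).** Need for INV is "for 45 mg/day IMU-838: 32" and "for placebo: 40" (per cent), with 80% power and "Global significance level: 0.05, 1-sided". The usual two-proportion formula with continuity correction gives 469 per arm, 938 in total. At an information rate of 0.2 this is 0.2 × 938 = 187.6, the stated 188. With 6% drop-out, 188 / 0.94 = 200, as stated. So 6% corresponds to 12 leavers in 200.

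**2. Effect of imputing failure.** Two assumptions make this an upper bound: every leaver is scored a failure, and leavers have the same INV risk as those who stay. For true rate p and drop-out d:

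- need for INV after imputation = (1 − d) × p + d
- INV-free after imputation = (1 − d) × (1 − p)

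For d = 0.06: IMU-838 0.94 × 0.32 + 0.06 = 0.361; placebo 0.94 × 0.40 + 0.06 = 0.436. The relative reduction is 1 − 0.3608 / 0.436 = 17.2%.

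For d = 0.09 on IMU-838 and 0.03 on placebo: 0.91 × 0.32 + 0.09 = 0.381; 0.97 × 0.40 + 0.03 = 0.418. The relative reduction is 1 − 0.3812 / 0.418 = 8.8%. INV-free: 0.6188 / 0.582 − 1 = 6.3%.

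| Drop-out, IMU-838 / placebo | Need for INV | Difference (points) | Relative reduction in need | Relative difference, INV-free |
|---|---|---|---|---|
| none imputed | 32.0% vs 40.0% | 8.0 | 20.0% | 13.3% |
| 6% / 6% | 36.1% vs 43.6% | 7.5 | 17.2% | 13.3% |
| 10% / 10% | 38.8% vs 46.0% | 7.2 | 15.7% | 13.3% |
| 8% / 4% | 37.4% vs 42.4% | 5.0 | 11.7% | 8.6% |
| 4% / 8% | 34.7% vs 44.8% | 10.1 | 22.5% | 18.3% |
| 9% / 3% | 38.1% vs 41.8% | 3.7 | 8.8% | 6.3% |
| 3% / 9% | 34.0% vs 45.4% | 11.4 | 25.0% | 20.8% |

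The unequal splits are assumptions, each with 12 leavers in total. On the INV-free scale the factor (1 − d) cancels when drop-out is equal, so the relative difference stays at 0.68 / 0.60 − 1 = 13.3%.

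**3. How unusual is 9 against 3?** If each of 12 leavers is equally likely to come from either arm, a split at least this uneven has probability 2 × (220 + 66 + 12 + 1) / 4096 = 0.146, about one in seven.

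**4. Sampling error for comparison.** With 100 per arm, the standard error of the difference is √(0.32 × 0.68 / 100 + 0.40 × 0.60 / 100) = 0.068, or 6.8 points.

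**The case against.** The case for leaving the text alone has five parts.

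- **Known data are used.** The sensitivity analyses draw on available INV and respiratory-failure information. This stands: a reader might infer that the plan ignores known outcomes, and it does not. But those analyses can use only what was collected, Section 16.4.2 does not name them as the basis of the activity decision, and the ICU one stops at discontinuation.
- **Contact is wider than survival.** A reader might infer that sites are confined to survival. The documents do not support that: Section 12.5 sets survival as a minimum and asks for EoS assessments, 17.2 asks for efforts to complete assessments, and Section 8.1 and footnote n want patient status on the EoS page even without a visit. Still, none of this tells sites to ask about INV, ICU, high-flow oxygen or ECMO by phone when the visit is missed. The telephone safety follow-up after Day 28 does include ICU status, but Table 3 marks oxygen supplementation and ECMO as not done by phone.
- **The failure rule may be deliberate.** It can be read as a conservative composite. Yet the stated endpoint is need for INV, and mortality receives the opposite treatment. The rule is also conservative only while placebo does not lose more patients; the 3% / 9% row shows it inflating the effect.
- **Few patients are affected.** Stopping study drug is not leaving the trial, patients who refuse all follow-up cannot be recovered, and the primary rule needs both early departure and no improvement. This stands and limits the size.
- **The shift is small beside sampling error.** This is true of the 0.5-point shift under equal drop-out. The 9% / 3% shift of 4.3 points (8.0 − 3.7) is also below one standard error. But it is systematic, may depend on treatment, and is avoidable where status can be obtained.

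**Conclusion.** The point holds as a gap in the main-analysis rules and an inconsistency in the contact rules. It concerns patients who leave or are lost on or before Day 13 without improvement (a wider group if the respiratory-failure and ICU wording is read broadly), who have not refused non-interventional follow-up, and whose status is known or retrievable.

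On the upper-bound assumptions, equal 6% drop-out costs half a point of absolute difference, and the relative effect falls only on the need-for-INV scale. Unequal drop-out matters more: 3.7 or 11.4 points instead of 8.0 for 9% against 3% either way.

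A reader might go on to infer that the rule would reverse the MA1 decision. The documents do not support that. The 9% / 3% case falls below the 10% criterion on both scales, but Section 16.4.2 has a third route at 5% with supporting endpoints, words its first route as near or above 20%, and requires an overall consistent pattern. Nor does it say clearly whether the relative difference is taken on need for INV or on INV-free patients.

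**What to change.** - **Section 16.3.2.** For the primary endpoint, respiratory failure and ICU duration, add the exception that mortality already has: impute only where status to Day 28 cannot be obtained. Keep failure imputation for unknown status, and run the present rule, regardless of known status, as a sensitivity analysis. State once, for all three endpoints, whether the Day 13 and no-improvement conditions apply jointly. The mortality text cites Section 12.4 for survival follow-up; the relevant text is in 12.5.
- **Synopsis, Section 8.1, Section 12.5 and footnote n.** Use one contact rule. Where the patient has not refused non-interventional follow-up, the site makes the Day 28 contact and records survival, INV (received or needed), ICU, high-flow oxygen and ECMO, with dates, on the EoS page.

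The cost is a few more questions in a call already foreseen, some fields on the EoS page and one clause in the analysis text. The drawback is that reports from relatives or outside physicians are less exact. That matters mainly for ICU dates and little for whether INV was received.

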12.6 Safety follow-up

Following the D28/EoS examination, the investigator will contact the patient regularly (at least once) by phone or email to obtain health data until Day 60. This should be documented as an unscheduled visit in the eCRF. The patients should be asked to return for an on-site visit if the investigator deems this necessary for follow-up.

13 Efficacy and baseline assessments and procedures

13.1 Demographics and other baseline assessments

During screening, demographics (including sex, age, height, weight, race, and ethnicity), presence of high-risk factors, a complete medical history, confirmation of SARS-CoV-2 infection status, and previous and concomitant therapy will be collected.

High risk factors include: Age ≥ 65 , cardiovascular disease (including hypertension), pre-existing pulmonary disease, diabetes, current treatment for malignancy or within the previous 3 years, immunosuppression (due to ongoing use of immunosuppressive drugs or existing disease leading

to impaired immune status), and body mass index (BMI). The BMI will be calculated from patient's height and weight.

13.2 Clinical disease severity assessment

The clinical disease severity will be assessed based on the WHO Ordinal Scale for Clinical Status [21, and [Table 4](#)]. The WHO scale is a 9-category ordinal scale and was developed to have a standardized measure of the COVID-19 disease severity. The scale comprises patient status (outpatient or hospitalized), virus status (infected yes or no), limitation of activities, oxygen support, and organ support. For the clinical assessment in this trial the WHO scale is slightly modified.

Table 4: Modified WHO Ordinal Scale for Clinical Status

Patient state	Descriptor	Score
Uninfected or no longer infectious	No clinical or virological evidence of infection	0
Mild Disease	Ambulatory, virus-positive, no limitation of activities	1
	Ambulatory, virus-positive, limitation of activities	2
Moderate Disease	Hospitalized, virus-positive, no oxygen therapy	3
	Hospitalized, virus-positive, oxygen by mask or nasal prongs	4
Severe Disease	Hospitalized, virus-positive, non-invasive ventilation or high-flow oxygen	5
	Hospitalized, virus-positive, intubation and mechanical ventilation	6
	Hospitalized, virus-positive, ventilation plus additional organ support (pressors, RRT, ECMO)	7
Dead	Death	8

ECMO = extracorporeal membrane oxygenation, RRT = renal replacement therapy.

Based on [\[21\]](#).

13.3 Clinical and patient status assessments

The following will be recorded regularly, once or twice daily, during the course of the trial (see [Table 3](#)):

- Hospitalization and ICU admissions
- Survival status
- Score assessment (WHO scale, see Section [13.2](#))
- Use of invasive and non-invasive ventilations, auxillary oxygen supplementation (including type of ventilation e.g., ECMO), and RRT
- Vital signs and temperature

- Respiratory rate and SpO₂ (see Section 13.4)
- Vasoactive therapy (type and dose)
- Confirmation of radiographic evidence of pulmonary infiltrates by chest X-ray or computer tomography (if done within the scope of routine clinical practice)
- Documentation of presence of any new viral or non-viral infection (e.g., if blood cultures and sputum gram stain and culture are done within the scope of routine clinical practice). Site of infection and source of culture will be documented.

